#### 6.3.2 Study follow-up

Both as-treated (AT) and intention-to-treat (ITT) analyses will be conducted with treatment defined as the index drug on the day of cohort entry. Because adherence in the real-world databases is expected to be much worse than in the trial, the AT analysis is the **primary** analysis, as it targets the relative hazard of outcomes on treatment.

For the AT analyses, the follow-up will start the day after initiation of apixaban and comparator and will continue until the earliest date of the following events:

- The first occurrence of the outcome of interest, unless otherwise specified for selected outcomes,
- The date of end of continuous registration in the database,
- End of the study period,
- Measured death event occurs,
- Nursing home admission

- Nursing home admissions are considered a censoring event because the data sources utilized typically provide little to no data on a patient, particularly on drug utilization, after admission. We will utilize this as an exclusion reason for cohorts for the same reason.
- The date of drug discontinuation, defined as the date of the last continuous treatment episode of the index drug (apixaban and comparator) plus a defined grace period (i.e., 10 days after the end of the last prescription's days' supply in main analyses).
- The date of augmentation or switching from exposure to comparator or vice versa or augmentation/switching to any other NOAC (e.g. switching from apixaban to rivaroxaban would be a censoring event);
  - A dosage change on the index treatment does not fulfill this criterion
  - An added treatment that is not part of the exposure or comparator group does not fulfill this criterion
- Treatment of current episode of VTE with thrombectomy, insertion of caval filter, or use of fibrinolytic agent (streptokinase, alteplase, reteplase, tenecteplase)

For the intention-to-treat (ITT) analyses, the censoring based on the augmentation/switching and treatment discontinuation will be replaced with a maximum allowed follow-up time of 365 days.

## 7. Initial Feasibility Analysis

Action report name:

For apixaban vs. warfarin

Optum- <https://bwh-dope.aetion.com/projects/details/1484/results/64537/result/0>

Marketscan- <https://bwh-dope.aetion.com/projects/details/1481/results/64536/result/0>

Medicare- <https://bwh-dope.aetion.com/projects/details/1483/results/64535/result/0>

Date conducted: 1/19/21

Complete Aetion feasibility analysis using age, sex, and CCI as the only covariates and the primary endpoint (Section 6.3.1) as the outcome. No measures of association will be computed nor will incidence rates stratified by treatment group.

- Report patient characteristics by treatment group
- Report summary parameters of study population

- Report median follow-up time by treatment group
- Report reasons for censoring in the overall study population

## 8. Initial Power Assessment

Action report name:

For apixaban vs. warfarin

Optum- <https://bwh-dope.aetion.com/projects/details/1484/results/64538/result/0>

Marketscan- <https://bwh-dope.aetion.com/projects/details/1481/results/64539/result/0>

Medicare- <https://bwh-dope.aetion.com/projects/details/1483/results/64540/result/0>

Date conducted: 1/19/2021

In order to complete the initial power analysis, the dummy outcome of a 90-day gap in database enrollment will be used. This outcome is used to ensure that no information on the comparative risks of the outcomes of interest are available at this stage. Complete a 1:1 PS-matched comparative analysis using this outcome. PS should include only 3 covariates: age, sex, and combined comorbidity index. Power calculations are based on the formulas from Chow et al. (2008).

- Stop analyses until feasibility and power are reviewed by primary investigators and FDA. Reviewers evaluate the results of the analyses described above in Sections 7 and 8, including numbers of patients, patient characteristics, follow-up time, and reasons for censoring by treatment group, as well as overall rates of outcomes and study power. These parameters are re-evaluated and reported in the subsequent sections, after incorporating feedback and refining the protocol.
- Stop analyses until balance and final power assessment are reviewed by primary investigators, FDA, and assigned members of advisory board.

|                                              |                  |                |            |
|----------------------------------------------|------------------|----------------|------------|
| Reviewed by PI:                              | [name] | Date reviewed: | 11/18/2020 |
| Reviewed by FDA:                             | [name]       | Date reviewed: | 11/29/2020 |
| Reasons for stopping analysis (if required): |                  |                |            |

## 9. Balance Assessment

**Action report links:**

Optum: <https://bwh-dope.aetion.com/projects/details/1484/results/64541/result/0>

Marketscan: <https://bwh-dope.aetion.com/projects/details/1481/results/64542/result/0>

Medicare: <https://bwh-dope.aetion.com/projects/details/1483/results/64543/result/0>

Date conducted: 1/19/2021

After review of initial feasibility and power analyses, complete creation of the remaining covariates from Section 6.2. Again, using the dummy outcome of a 90-day gap in database enrollment, complete a 1:1 PS-matched analysis. The PS should include the complete list of covariates.

- Provide plot of PS distributions stratified by treatment group.

Note- Please refer to **Appendix B**.

- Report covariate balance after matching.

Note- For Table 1, please refer to **Appendix B**.

- Report reasons for censoring by treatment group.

|  | Overall | Referent | Exposure |
|--|---------|----------|----------|
|--|---------|----------|----------|

|                                                                                                                               |                |                |                |
|-------------------------------------------------------------------------------------------------------------------------------|----------------|----------------|----------------|
| Dummy outcome                                                                                                                 | 67 (0.94%)     | 25 (0.70%)     | 42 (1.18%)     |
| Death                                                                                                                         | 103 (1.44%)    | 49 (1.37%)     | 54 (1.51%)     |
| Start of an additional exposure                                                                                               | 232 (3.25%)    | 175 (4.90%)    | 57 (1.60%)     |
| End of index exposure                                                                                                         | 4,701 (65.84%) | 2,202 (61.68%) | 2,499 (70.00%) |
| Specified date reached                                                                                                        | 857 (12.00%)   | 424 (11.88%)   | 433 (12.13%)   |
| End of patient enrollment                                                                                                     | 425 (5.95%)    | 198 (5.55%)    | 227 (6.36%)    |
| Switch to NOACs (for censoring) + nursing home admission + thrombectomy, insertion of caval filter, use of fibrinolytic agent | 755 (10.57%)   | 497 (13.92%)   | 258 (7.23%)    |

- Report follow-up time by treatment group.

| Median Follow-Up Time (Days) [IQR] |                 |              |             |
|------------------------------------|-----------------|--------------|-------------|
| Patient Group                      | Optum           | Marketscan   | Medicare    |
| Overall Patient Population         | 82.5 [38-174.5] | 96 [38-186]  | 74 [38-170] |
| Referent                           | 72 [37-189]     | 88 [38-171]  | 73 [38-161] |
| Exposure                           | 96.5 [38-155]   | 100 [38-195] | 78 [38-183] |

- Report overall risk of the primary outcome.

|                         | Optum | Marketscan | Medicare | Pooled |
|-------------------------|-------|------------|----------|--------|
| Risk per 1,000 patients | 12.93 | 13.13      | 14.66    | 13.74  |

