### 6.2 Covariates:

- Age
- Sex
- Combined Comorbidity Index (CCI), measured over the baseline covariate assessment period, defined as 180 days prior to and including index date

Covariates listed above represent only a small subset of covariates that will ultimately be controlled for in the design and analysis. We use the covariates above only for initial feasibility analyses to judge whether there is likely to be sufficient overlap between treatment groups to proceed with the study. Remaining covariates are defined only after the study has passed the initial feasibility analysis and the initial power assessment and are listed in Table 1 (**Appendix B**).

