| • Acute symptomatic PE with evidence of thrombosis demonstrated by imaging as follows:
- an intraluminal filling defect in segmental or more proximal branches on spiral computed tomography (CT) scan; or
- an intraluminal filling defect or a sudden cutoff of vessels more than 2.5 mm in diameter on the pulmonary angiogram; or
- a perfusion defect of at least 75% of a segment with a local normal ventilation result (high probability) on ventilation/perfusion lung scan (VPLS) | Measured 180 days prior to and including day of drug initiation in any diagnosis position and in an inpatient or ED care setting

Pulmonary embolism (PE):
ICD-9 Dx: 415.xx
ICD-10 Dx: I26.xx                                            |                                                                                                                                                                                                                                                                                  |                                                                                                                                                                                                                                                                                                                                                                                                                                                                                                                    |

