# Appendix B

|                                                                                            |               |               |         |               |               |         |               |               |           |               |               |         |
|--------------------------------------------------------------------------------------------|---------------|---------------|---------|---------------|---------------|---------|---------------|---------------|-----------|---------------|---------------|---------|
| Non-Frailty; n (%)                                                                         | 607 (41.2%)   | 1,297 (46.6%) | -0.11   | 986 (40.0%)   | 1,622 (41.9%) | -0.04   | 219 (4.4%)    | 103 (3.0%)    | 0.07      | 1,812 (20.3%) | 3,022 (30.0%) | -0.22   |
| Frailty Score (mean): Empirical Version 365 days, v2                                       |               |               |         |               |               |         |               |               |           |               |               |         |
| ...mean (sd)                                                                               | 0.17 (0.06)   | 0.17 (0.06)   | 0.00    | 0.16 (0.05)   | 0.15 (0.05)   | 0.20    | 0.10 (0.08)   | 0.09 (0.07)   | 0.13      | 0.13 (0.07)   | 0.14 (0.06)   | -0.15   |
| Healthcare Utilization                                                              |               |               |         |               |               |         |               |               |           |               |               |         |
| Any hospitalization; n (%)                                                                 | 1,342 (91.2%) | 2,517 (90.4%) | 0.03    | 2,456 (99.7%) | 3,872 (99.9%) | -0.04   | 4,571 (91.7%) | 2,940 (86.3%) | 0.17      | 8,369 (93.8%) | 9,329 (92.7%) | 0.04    |
| Any hospitalization within prior 30 days; n (%)                                            | 1,218 (82.7%) | 2,064 (74.2%) | 0.21    | 2,325 (94.4%) | 3,266 (84.3%) | 0.33    | 3,605 (72.3%) | 2,224 (65.3%) | 0.15      | 7148 (80.1%)  | 7554 (75.1%)  | 0.12    |
| Any hospitalization during prior 31-180 days; n (%)                                        | 210 (14.3%)   | 596 (21.4%)   | -0.19   | 279 (11.3%)   | 830 (21.4%)   | -0.28   | 1,509 (30.3%) | 1,094 (32.1%) | -0.04     | 1998 (22.4%)  | 2520 (25.0%)  | -0.06   |

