# Appendix B

|                                                                                            |               |               |           |               |               |           |               |               |           |               |               |         |
|--------------------------------------------------------------------------------------------|---------------|---------------|-----------|---------------|---------------|-----------|---------------|---------------|-----------|---------------|---------------|---------|
| Non-Frailty; n (%)                                                                         | 206 (42.0%)   | 210 (42.9%)   | -0.02     | 581 (42.1%)   | 583 (42.2%)   | 0.00      | 57 (3.4%)     | 47 (2.8%)     | 0.03      | 844 (23.6%)   | 840 (23.5%)   | 0.00    |
| Frailty Score (mean): Empirical Version
365 days, v2                                    |               |               |           |               |               |           |               |               |           |               |               |         |
| ...mean (sd)                                                                               | 0.18 (0.06)   | 0.18 (0.06)   | 0.00      | 0.15 (0.05)   | 0.15 (0.05)   | 0.00      | 0.10 (0.07)   | 0.10 (0.08)   | 0.00      | 0.13 (0.06)   | 0.13 (0.07)   | 0.00    |
| Healthcare Utilization                                                                     |               |               |           |               |               |           |               |               |           |               |               |         |
| Any hospitalization; n (%)                                                                 | 438 (89.4%)   | 453 (92.4%)   | -0.10     | 1,379 (99.9%) | 1,380 (99.9%) | 0.00      | 1,564 (92.1%) | 1,555 (91.5%) | 0.02      | 3,381 (94.7%) | 3,388 (94.9%) | -0.01   |
| Any hospitalization within prior 30 days; n (%)                                            | 374 (76.3%)   | 364 (74.3%)   | 0.05      | 1,287 (93.2%) | 1,302 (94.3%) | -0.05     | 1,204 (70.9%) | 1,229 (72.3%) | -0.03     | 2865 (80.3%)  | 2895 (81.1%)  | -0.02   |
| Any hospitalization during prior 31-180 days; n (%)                                        | 101 (20.6%)   | 121 (24.7%)   | -0.10     | 185 (13.4%)   | 166 (12.0%)   | 0.04      | 565 (33.3%)   | 546 (32.1%)   | 0.03      | 851 (23.8%)   | 833 (23.3%)   | 0.01    |

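### The propensity score has no direct covariate for time from the qualifying VTE to drug start, or for its care setting; the any-cause proxies balance after matching but are too coarse to rule out residual confounding

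*Combined protocol and SAP*

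**What the plan says.** For both DVT and PE, Appendix A defines the qualifying diagnosis as follows: "Measured 180 days prior to and including day of drug initiation in any diagnosis position and in an inpatient or ED care setting". A patient whose clot was diagnosed on the day of drug start and one whose clot was diagnosed five months earlier are therefore equally eligible.

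Section 9 sets the content of the score: "The PS should include the complete list of covariates". Section 6.2 says that the covariates beyond age, sex and comorbidity index "are listed in Table 1" in Appendix B.

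Table 1 carries these rows bearing on the index event:
- PE yes/no and DVT yes/no, without dates.
- Any hospitalization, and hospitalization in the prior 30 days and in the prior 31-180 days, for any cause.
- Numbers of hospitalizations, hospital days and ED visits.

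It has no row for the interval from the qualifying VTE to drug start, and none for whether the qualifying code was inpatient or ED.

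**The concern.** The trial being emulated concerned acute VTE and limited prior heparin and VKA treatment before study drug. Appendix A marks both of those limits as not applicable here, so nothing in the cohort definition holds the delay short except the 180-day window. If recurrence risk falls with time since the clot (my assumption; the documents give no figure), the interval is a baseline confounder wherever it is also related to drug choice.

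The unmatched Table 1 gives indirect reason to think it may be. For the row "Any hospitalization within prior 30 days; n", the MarketScan entry reads "2,325 (94.4%) | 3,266 (84.3%) | 0.33" (warfarin, apixaban, standardized difference) and the pooled entry "7148 (80.1%) | 7554 (75.1%) | 0.12". The pooled 31-180 day row leans the other way: "1998 (22.4%) | 2520 (25.0%) | -0.06". Under the primary as-treated analysis, median follow-up by arm is only 72 to 100 days, so where follow-up starts relative to the clot could matter for the hazard ratio.

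**Working it through.** **1. The plan's own figure.** Section 10 gives pooled power 0.9652 from 7,140 matched patients at 13.74 per 1,000, i.e. 98.1036 events. Φ(√(98.1036/4) × ln(1.8/0.84) − 1.96) = Φ(4.952 × 0.7621 − 1.96) = Φ(1.814) = 0.965. It reproduces and is not in dispute.

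**2. Do the event flags carry timing?** PE is present in 99.6% to 100% of every matched arm, so it hardly varies. DVT is 51.5% vs 51.4% matched and is undated. Neither dates the event.

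**3. Proxies before matching.** The standardized difference is (p1 − p2)/√[(p1q1 + p2q2)/2], warfarin minus apixaban. For MarketScan, 30 days: (0.9436 − 0.8431)/√[(0.0532 + 0.1323)/2] = 0.33, as printed.

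| Unmatched | Admission ≤30 d, W vs A | SMD | Admission 31-180 d, W vs A | SMD |
|---|---|---|---|---|
| MarketScan | 94.4% vs 84.3% | 0.33 | 11.3% vs 21.4% | -0.28 |
| Optum | 82.7% vs 74.2% | 0.21 | 14.3% vs 21.4% | -0.19 |
| Medicare | 72.3% vs 65.3% | 0.15 | 30.3% vs 32.1% | -0.04 |

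**4. How much of the Medicare gap is timing?**
- No admission within 30 days: 1,378/4,983 (27.7%) vs 1,182/3,406 (34.7%), a gap of 7.0 points.
- No baseline admission at all: 4,983 − 4,571 = 412 (8.3%) vs 3,406 − 2,940 = 466 (13.7%), a gap of 5.4 points.
- An admission, but none within 30 days: 966 (19.4%) vs 716 (21.0%), a gap of 1.6 points.

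Most of the Medicare difference is therefore patients never admitted, who may have had a recent ED event. MarketScan, where 99.7% and 99.9% were admitted at some point, gives the cleanest timing signal.

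**5. Proxies after matching** (SMDs as printed).

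| Matched | ≤30 d, W vs A | SMD | 31-180 d, W vs A | SMD |
|---|---|---|---|---|
| MarketScan | 93.2% vs 94.3% | -0.05 | 13.4% vs 12.0% | 0.04 |
| Optum | 76.3% vs 74.3% | 0.05 | 20.6% vs 24.7% | -0.10 |
| Medicare | 70.9% vs 72.3% | -0.03 | 33.3% vs 32.1% | 0.03 |
| Pooled | 80.3% vs 81.1% | -0.02 | 23.8% vs 23.3% | 0.01 |

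Pooled, patients with no admission in 30 days number 3,570 − 2,865 = 705 (19.7%) on warfarin and 3,570 − 2,895 = 675 (18.9%) on apixaban. Optum also keeps a small difference in any admission: 89.4% vs 92.4%, SMD -0.10.

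**6. What the proxies cannot see.** Matched patients with no baseline admission: 7,140 − 3,381 − 3,388 = 371 (189 warfarin, 182 apixaban). If that row covers the same window as entry, all of them qualified through an ED code, and nothing in Table 1 dates it.

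**7. Effect of the visible gap.** Suppose patients with an admission within 30 days have R times the recurrence rate of the others (R = 2 to 5 is an assumption). The hazard ratio is then multiplied by about [1 + pA(R−1)]/[1 + pW(R−1)].
- Unmatched pooled (pW 0.8014, pA 0.7507): 1.7507/1.8014 = 0.97 at R = 2; 4.0028/4.2056 = 0.95 at R = 5.
- Matched pooled (pW 0.8025, pA 0.8109): 1.8109/1.8025 = 1.005 at R = 2; 4.2437/4.2101 = 1.008 at R = 5.

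**The case against.** The strongest reply is that the effect is estimated in the matched cohort, where the pooled 30-day row reads "2865 (80.3%) | 2895 (81.1%) | -0.02". The gap seen before matching is gone, and what is left leans slightly the other way. The utilization counts also balance (mean ED visits 2.77 vs 2.78), and Optum, the one database with remnants, supplies only 980 of 7,140 patients. All of this stands. It shows balance on any-cause admissions, not on the VTE interval itself.

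Three stronger readings are tempting, and the documents do not support them.
- *Apixaban patients start later after their VTE.* No section reports VTE-to-start time by arm. The inference rests on unmatched any-cause admissions, which need not be the VTE admission.
- *The hazard ratio is biased by 4-10%.* That follows if 15% of one matched arm and 20-25% of the other are late starters, with a 3- to 5-fold early hazard: (0.85×3 + 0.15)/(0.80×3 + 0.20) = 2.7/2.6 = 1.04, and (0.85×5 + 0.15)/(0.75×5 + 0.25) = 4.4/4.0 = 1.10. But 5-10 points is one to two times the unmatched pooled gap, while the matched proxy gap is 0.8 points. Even at a true hazard ratio of 0.92 (about 0.84 × 1.10), power would be Φ(4.952 × ln(1.8/0.92) − 1.96), about 91%.
- *The gap matters equally under any entry window.* With a short window the later intervals are empty and most of the argument goes.

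**Conclusion.** The omission is real: the score has no direct measure of time since the qualifying VTE or of its setting, although entry spans 0-180 days and two settings. The listed proxies differ by drug before matching and balance when pooled after it, apart from small Optum remnants. They are too coarse to show that the interval itself is balanced, so residual confounding cannot be excluded.

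Its size is unknown. The visible matched gap implies less than 1% on the hazard ratio for R from 2 to 5. Any larger figure needs an imbalance within the proxy windows, or among ED-only patients, that no table shows. No stated power figure is wrong. This is a worthwhile, low-cost correction, not evidence of a biased result.

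**What to change.** Before Section 13, and in each database:
1. Add to the propensity score categorical days from the start of the current VTE episode to drug start, with categories fitted to the final entry window. Define the start as the first qualifying code of that episode. The most recent code, in any diagnosis position, could be a later admission carrying the old diagnosis and would reset the clock.
2. Add inpatient versus ED setting of that same code.
3. Re-match, report both variables by arm before and after matching in Table 1, and restate matched N and power in Section 10.

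An acute cor pulmonale flag is not requested, because no table shows an imbalance on it.

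The entry criterion already uses the code's date and setting, so the data are to hand. Section 9 runs on a dummy outcome and Section 13 is blank, so the change can be made without sight of comparative results. The cost is a re-run of the score and the loss of some matched pairs, possibly more in the database whose pre-match c-statistic is 0.938.

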## 10. Final Power Assessment

Date conducted: 12/16/20

- Re-calculate power in the appropriate excel table, using the revised number of matched patients from the PS-match in Section 9. All other parameters in the table should be the same as in Section 8.
  - Pooled

Effectiveness research with Real World Data to support FDA's regulatory decision making

| Non-inferiority Analysis |             |
|---------------------------------|-------------|
| Number of patients matched      | 7,140       |
| Reference                       | 3,570       |
| Exposed                         | 3,570       |
| Risk per 1,000 patients         | 13.74       |
| HR from RCT                     | 0.84        |
| Alpha (2-sided)                 | 0.05        |
| Non-inferiority margin          | 1.8         |
|                                 |             |
| Number of events expected       | 98.1036     |
| Power                           | 0.965194245 |

- Optum

| Non-inferiority Analysis |             |
|---------------------------------|-------------|
| Number of patients matched      | 980         |
| Reference                       | 490         |
| Exposed                         | 490         |
| Risk per 1,000 patients         | 12.93       |
| HR from RCT                     | 0.84        |
| Alpha (2-sided)                 | 0.05        |
| Non-inferiority margin          | 1.8         |
|                                 |             |
| Number of events expected       | 12.6714     |
| Power                           | 0.273097221 |

○ Marketscan

| Non-inferiority Analysis |             |
|---------------------------------|-------------|
| Number of patients matched      | 2,762       |
| Reference                       | 1,381       |
| Exposed                         | 1,381       |
| Risk per 1,000 patients         | 13.13       |
| Assumed HR from RCT             | 0.84        |
| Alpha (2-sided)                 | 0.05        |
| Non-inferiority margin          | 1.8         |
|                                 |             |
| Number of events expected       | 36.26506    |
| Power                           | 0.631133873 |

o Medicare

| Non-inferiority Analysis   |             |
|----------------------------|-------------|
| Number of patients matched | 3,398       |
| Reference                  | 1,699       |
| Exposed                    | 1,699       |
| Risk per 1,000 patients    | 14.66       |
| Assumed HR from RCT        | 0.84        |
| Alpha (2-sided)            | 0.05        |
| Non-inferiority margin     | 1.8         |
|                            |             |
| Number of events expected  | 49.81468    |
| Power                      | 0.767185633 |

- Stop analyses until balance and final power assessment are reviewed by primary investigators, FDA, and assigned members of advisory board.

|                                              |              |                |            |
|----------------------------------------------|--------------|----------------|------------|
| Reviewed by PI:                              | [name] | Date reviewed: | 12/24/2020 |
| Reviewed by FDA:                             | [name]   | Date reviewed: | 01/18/2020 |
| Reasons for stopping analysis (if required): |              |                |            |

